6.2.3. Vital Signs Data

Absolute values and changes from baseline (as defined in Section 3.2.3) in supine systolic and diastolic blood pressure and pulse rate will be listed, and summarized by treatment and

timepoint, according to sponsor reporting standards using the safety population defined in Section 4. Tables will be paged by parameter.

Mean absolute values and mean changes from baseline for systolic and diastolic blood pressure and pulse rate will be plotted against time point. On each plot, there will be 1 line for each treatment with all treatments on the same plot. Corresponding individual participant plots of changes from baseline will also be produced for each treatment.

Maximum decrease from baseline for supine systolic and diastolic blood pressures and respiratory rate and maximum increase from baseline for supine pulse rate and temperature will be summarized by treatment, according to sponsor reporting standards.

Maximum and minimum absolute values and changes from baseline (as defined in Section 3.2.3) for supine vital signs will also be summarized descriptively by treatment using categories as defined in Appendix 2. Numbers and percentages of participants meeting the categorical criteria will be provided. All planned and unplanned post dose time points will be counted in these categorical summaries. All values meeting the criteria of potential clinical concern will be listed.

Individual participant profiles will be created for those participants meeting the sponsor abnormality criteria – including absolute values, change from baseline and percent change from baseline.

Values meeting the categorical criteria occurring pre-dose on Day 1 for each period starting with Period 2, will be attributed to the dose from the previous period (e.g., an occurrence pre-dose at Period 2 Day 1 will be attributed to the Period 1 dose).

Data collected at screening that are used for inclusion/exclusion criteria, will be considered source data, and will not be required to be reported, unless otherwise noted. Unplanned assessment will be listed but will be excluded from safety summary except for categorical summaries.

6.2.4. Electrocardiogram Data

Absolute values and changes from baseline in QT, heart rate, QTcF, PR and QRS will be summarized by treatment and timepoint using sponsor reporting standards, using the safety analysis set defined in Section 4. Baseline is as defined in Section 3.2.4. Tables will be paged by parameter.

Mean changes from baseline in QT, heart rate and QTcF will be plotted against time postdose. On each plot there will be one line for each treatment. Corresponding individual plots of changes from baseline will also be produced for each treatment.

Changes from baseline in QTcF will also be plotted separately against drug concentrations of PF-07817883. This will be a scatter plot for all observations where QTcF and drug concentration are recorded. Different symbols will be used for each treatment.

Maximum increase from baseline for QTcF, heart rate, PR and QRS values will be summarized by treatment according to sponsor reporting standards.

ECG endpoints and changes from baseline (QTcF [1], PR and QRS) will also be summarized descriptively by treatment (if applicable) using categories as defined in Appendix 2. Numbers and percentages of participants meeting the categorical criteria will be provided. All planned and unplanned postdose time points will be counted in these categorical summaries. The frequency of uncorrected QT values above 500 ms will also be tabulated.

Individual participant profiles will be created for those participants meeting the sponsor's abnormality criteria – including absolute values, change from baseline and percent change from baseline.

Values meeting the categorical criteria occurring pre-dose on Day 1 for each period starting with Period 2, will be attributed to the treatment from the previous period (e.g., for cohort 1, an occurrence pre-dose at Period 2 Day 1 will be attributed to the Period 1 dose).

Listings of participants with any single post-dose value >500msec will also be produced for QTcF.

Data collected at screening that are used for inclusion/exclusion criteria, will be considered source data, and will not be required to be reported, unless otherwise noted. Unplanned assessments will be listed but will be excluded from safety summary except for categorical summaries.

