4. STUDY DESIGN

4.1. Overall Design

This is a Phase 1, open-label, randomized, 4-period, 4-sequence crossover study in healthy adult participants evaluating the rBA of 3 new PF-07817883 test oral formulation(s) compared to PF-07817883 reference oral formulation. Approximately 12 participants will be enrolled in this study with approximately equal number of participants randomized to 1 of 4 sequences (Table 2). The new formulations used for each treatment as defined in Table 2 will be decided based on the availability of new formulations.

Table 2. Study Design

Sequence	Period 1	Period 2	Period 3	Period 4
1 (n=3)	A	В	C	D
2 (n=3)	В	D	A	C
3 (n=3)	C	A	D	В
4 (n=3)	D	С	В	A

Treatment A = PF-07817883 300 mg reference formulation, fasted, DP-006067, 23-DP-01449

Treatment B = PF-07817883 300 mg test formulation 1, fasted, DP-006067, 23-DP-01526

Treatment C = PF-07817883 300 mg test formulation 2, fasted, DP-006973, 23-DP-01687

Treatment D = PF-07817883 300 mg test formulation 3, fasted, DP-006974, 23-DP-01696

Healthy participants will be screened to determine eligibility within 28 days prior to study treatment. Participants will report to the CRU on Period 1 Day -1 (Study Day -1) and will be required to stay at the CRU until discharge. The participants will remain confined at the CRU until all assessments in all periods are complete.

In each period on Day 1, following an overnight fast of ~10h, participants will receive one of the treatments as defined in Table 2. Serial plasma PK samples will be collected up to 48 hours following the dose, at times outlined in the SoA. Participants will also complete a drug-product acceptability questionnaire shortly after receiving PF-07817883 in each period. At least 48 hours of washout between the doses of PF-07817883 administered to a participant in consecutive periods will be implemented. Dosing in the subsequent periods can take place immediately following the last PK sample collection of a period (SoA, Section 5.3).

A follow-up (which may be a phone call) will be made to participants approximately 28 to 35 days from administration of the final dose of study intervention.

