9. STATISTICAL CONSIDERATIONS

Detailed methodology for summary and statistical analyses of the data collected in this study is outlined here and further detailed in the SAP, which will be maintained by the sponsor. The SAP may modify what is outlined in the protocol where appropriate; however, any major modifications of the primary endpoint definitions or their analyses will also be reflected in a protocol amendment.

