9.3.1. General Considerations

All data will be presented by treatment groups and by total. Descriptive statistics will be provided. The following listing of individual participants data may also be produced: Disposition Events, Potentially Important Protocol Deviations, Subject Evaluation Groups, Demographic Information, Concomitant Medications, Compliance with Study Intervention.

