2.1. Modifications to the Analysis Plan Described in the Protocol

No modifications.

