5.2. General Methods

Unless otherwise stated, all summaries and plots will be presented by treatment.

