5.2.2. Analyses for Categorical Endpoints

Categorical variables will be presented using summary statistics: number of observations and percentages.

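### SAP 6.2.4 tabulates ECG change by formulation, but each completer's only scheduled post-dose ECG follows all four formulations, and the total asked for in Protocol 9.3.1 is not carried into the ECG tables

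*SAP*

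**What the plan says.** **Planned ECG and lab outputs.** SAP 6.2.4 states: "Absolute values and changes from baseline in QT, heart rate, QTcF, PR and QRS will be summarized by treatment and timepoint". It adds maximum increases by treatment, mean-change plots with a line per treatment, a scatter of QTcF change against drug concentration with a symbol per treatment, and categorical tables, of which it says "Numbers and percentages of participants meeting the categorical criteria will be provided". Protocol 9.3.5.1 likewise asks for ECG change by treatment and time. For labs, SAP 6.2.2 plans summaries both by treatment and overall, and does not name change from baseline.

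**Presentation.** Protocol 9.3.1 says "All data will be presented by treatment groups and by total". SAP 5.2 says "Unless otherwise stated, all summaries and plots will be presented by treatment", and SAP 6.2.4 names no overall ECG summary. SAP 2.1, on departures from the protocol, reads "No modifications".

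**Schedule and baselines.** In the Schedule of Activities (Protocol 1.3), ECGs fall at screening, before dosing on Period 1 Day 1, on Day 3 of the last period, and at early termination (ET). Safety labs fall at screening, on Day -1 (which occurs only before Period 1), on Day 3 of the last period, and at ET. SAP 3.2.4 takes the ECG baseline before dosing on Period 1 Day 1, and SAP 3.2.2 takes the lab baseline on Day -1. Protocol 4.1 sets the dosing interval: "At least 48 hours of washout between the doses of PF-07817883 administered to a participant in consecutive periods will be implemented".

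**Attribution rules.** SAP 6.2.2 assigns lab abnormalities on Day -1 of Period 2 onward to the previous period's dose. SAP 6.2.4 does the same for pre-dose Day 1 ECG values of Period 2 onward, with an example that refers to a cohort 1.

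**The concern.** A column of ECG change headed with one formulation will be read as the change after that formulation. Under this schedule it is the change after the whole course of doses, shown under whichever formulation came last. A shift that began after an earlier dose and persisted to the end would be displayed under the wrong product.

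The summary that the data can support, one change from before dose 1 to the end of dosing across all participants assessed, is the one that SAP 6.2.4 leaves out. The number of observations in each table will show that the columns are small. It will not show that the change spans four formulations.

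Safety of the formulations is the only secondary objective, and the protocol says that the results will inform formulation selection, so the labels should be right even though these outputs are descriptive.

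**Working it through.** **Inputs.** Sequences and numbers per sequence: Protocol Table 2 and 9.5. ECG and lab visits: Schedule of Activities. Baselines: SAP 3.2.2 and 3.2.4. Dosing interval: Protocol 4.1.

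**1. The plan's own numbers.** 4 sequences × 3 = 12 randomized; 4 × 2 = 8 completers. Both agree with Protocol 9.5.

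**2. Who fills each column.** A completer's scheduled post-dose ECG is in Period 4, so it falls under the Period 4 formulation:

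| Sequence | Order | Period 4 formulation | Post-dose ECGs, 12 completers | Post-dose ECGs, 8 completers |
|---|---|---|---|---|
| 1 | A B C D | D | 3 | 2 |
| 2 | B D A C | C | 3 | 2 |
| 3 | C A D B | B | 3 | 2 |
| 4 | D C B A | A | 3 | 2 |

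Each formulation column is exactly one sequence. Among completers, formulation and sequence cannot be separated, and the columns contain different people, so the crossover's within-participant comparison is lost.

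ET records add to this. With 8 completers and 0 to 4 ET records there are 8 to 12 records, or 8/4 = 2 to 12/4 = 3 per column on average.

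**3. What the change measures.** Dose 4 comes at least 3 × 48 = 144 h after dose 1. The ECG is 48 h later, so at least 144 + 48 = 192 h after dose 1. The change runs from before dose 1 to that point and covers A, B, C and D in every completer.

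**4. Coverage.** With 12 completers there are 12 × 4 = 48 doses and 12 scheduled post-dose ECGs; 36/48 = 75% of doses have none before the next dose. With 8 completers, 24/32 = 75%. The counts for labs are the same.

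**5. Categorical tables.** SAP 5.2.2 says "Categorical variables will be presented using summary statistics: number of observations and percentages", and neither it nor SAP 6.2.4 states the denominator. For one participant meeting a criterion at the scheduled ECG:

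| Denominator | Column, 12 completers | Column, 8 completers | Overall, 12 | Overall, 8 |
|---|---|---|---|---|
| Those assessed (completers only) | 1/3 = 33% | 1/2 = 50% | 1/12 = 8% | 1/8 = 13% |
| Those treated with that formulation | about 1/12 = 8% | about 1/8 = 13% | 1/12 = 8% | 1/8 = 13% |

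The contrast exists only in the first row.

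**6. Precision, for scale only, since no interval is planned for ECG change.** The 90% half-width of a mean change is t(0.95, n-1)/√n standard deviations of the change. Per column it is 1.69 at n = 3 and 4.46 at n = 2. Overall it is 0.52 at n = 12 and 0.67 at n = 8.

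**7. QTcF-concentration scatter.** Completers' scheduled post-baseline points (12 or 8) all lie at 48 h. Protocol 4.2 expects the washout to bring concentration below 5% of Cmax, so these points cover very little of the concentration range.

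**8. Attribution rules against the schedule.** Day -1 labs in Periods 2 to 4: not scheduled. Pre-dose Day 1 ECGs in Periods 2 to 4: marked as not required. Cohort 1: Table 2 has no cohorts. Neither rule covers the one scheduled post-dose value that will exist.

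**The case against.** The other side has a fair case. Protocol 4.2 explains that post-dose labs and ECGs in each period were left out on purpose, to limit burden, because the formulations should have very similar safety. All four are 300 mg immediate-release tablets of the same drug. SAP 5.1 plans no hypothesis tests and no decision rules. SAP 3.2.4 does state where the ECG baseline lies, and assigning an observation to the most recent treatment is already the rule for adverse events (SAP 3.2.1). Nothing in the documents points to a lasting ECG or lab shift specific to one formulation. All of this stands, and it makes the point small. It does not make the by-treatment change column mean what its label says.

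Several stronger readings are tempting, and the documents do not support them:

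- *Lab change from baseline is tabulated by formulation with no overall view.* SAP 6.2.2 does not name lab change from baseline and already includes an overall summary. Only the attribution of the by-treatment lab summary is affected.
- *The ECG tables will have no total.* SAP 6.2.4 omits it, but Protocol 9.3.1 asks for it, and the sponsor reporting standards cited for layout are not available here. The gap shown is in the SAP text.
- *One case will read as 33% or 50% under a formulation.* That needs the number assessed as denominator. Unplanned post-dose ECGs also count in the categorical tables, which are by treatment only if applicable.
- *The scatter should be dropped.* It takes every observation with both QTcF and concentration, including ET, where both are scheduled. A footnote is enough.
- *The 75% of doses without a scheduled ECG or lab is an analysis error.* It describes a deliberate schedule, and no change of wording alters it.

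**Conclusion.** The point holds for ECG as SAP 6.2.4 is written, and for labs as a matter of attribution only. Among completers, each by-treatment ECG change column is one sequence group of about 3 (2 with 8 completers), confounded with sequence, with a change that spans all four formulations. The SAP text also omits the ECG total that Protocol 9.3.1 asks for, while SAP 2.1 declares no departure. The attribution rules in SAP 6.2.2 and 6.2.4 address assessments that are not scheduled.

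Severity is minor. Only descriptive secondary safety outputs are touched. The primary PK analysis, treatment-emergent adverse events and vital signs (pre-dose and with their own baseline in each period) are unaffected.

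The conclusion rests on two assumptions. The first is that the Period 4 Day 3 value is placed under the last formulation received; this is inferred from the by-treatment layout, the previous-period rules and the adverse-event rule, and is not stated. The second is that the counts refer to completers and scheduled assessments, to which ET and unplanned records may add. The size of any distortion in the categorical percentages depends on a denominator that the SAP does not state.

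**What to change.** Change SAP wording only:

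1. In 6.2.4, add an overall presentation beside the by-treatment one. Make the overall change from baseline to Period 4 Day 3 or ET the main ECG summary, and state that the denominator is the number assessed.
2. Footnote the by-treatment ECG and lab displays that are kept: treatment is the last formulation received; the ECG change is from before dose 1 and spans all doses received; the display does not compare formulations.
3. Keep the QTcF-concentration scatter and the time plots, with a footnote that completers' scheduled post-baseline points are at 48 h after the Period 4 dose only.
4. Reconcile the attribution rules in 6.2.2 (Day -1 labs of Period 2 onward) and 6.2.4 (pre-dose Day 1 ECGs of Period 2 onward, and the reference to a cohort) with the Schedule of Activities.

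The cost is a few sentences, one overall ECG column and some footnotes, with no added visits, samples or participants. Keeping the by-treatment tables satisfies Protocol 9.3.5.1, and adding the total brings the SAP into line with Protocol 9.3.1. No protocol amendment is needed: Protocol 9 says "The SAP may modify what is outlined in the protocol where appropriate" and calls for an amendment only for major changes to the primary endpoint definitions or their analyses. The downside is less emphasis on ECG change by formulation, which this schedule cannot support.

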8.3.3. Electrocardiograms

Standard 12-lead ECGs will be collected at times specified in the SoA section of this protocol using an ECG system that automatically calculates the HR and measures PR, QT, QTcF, and QRS intervals. All scheduled ECGs should be performed after the participant has rested quietly for at least 5 minutes in a supine position.

To ensure safety of the participants, a qualified individual at the investigator site will make comparisons to baseline measurements. Additional ECG monitoring will occur if a) a postdose QTcF interval is increased by ≥60 ms from the baseline and is >450 ms; or b) an absolute QT value is ≥500 ms for any scheduled ECG. If either of these conditions occurs, then 2 additional ECGs will be collected approximately 2 to 4 minutes apart to confirm the original measurement. If the QTcF values from these repeated ECGs remain above the threshold value, then a single ECG must be repeated at least hourly until QTc values from 2 successive ECGs fall below the threshold value that triggered the repeat measurement.

If a) a postdose QTcF interval remains ≥60 ms from the baseline and is >450 ms; or b) an absolute QT value is ≥500 ms for any scheduled ECG for greater than 4 hours (or sooner, at the discretion of the investigator); or c) QTcF value get progressively longer, the participant should undergo continuous ECG monitoring. A cardiologist should be consulted if QTcF values do not return to less than the criteria listed above after 8 hours of monitoring (or sooner, at the discretion of the investigator).

In some cases, it may be appropriate to repeat abnormal ECGs to rule out improper lead placement as contributing to the ECG abnormality. It is important that leads be placed in the same positions each time in order to achieve precise ECG recordings. If a machine-read QTc value is prolonged, as defined above, repeat measurements may not be necessary if a qualified medical provider's interpretation determines that the QTcF values are in the acceptable range.

ECG values of potential clinical concern are listed in Appendix 7.

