3.2.3. Vital Signs Data

Single supine blood pressure and pulse rate measurements will be taken at times detailed in the SoA given in the protocol.

Baseline for these measures will be defined as the last pre-dose measurement in each study period.

The following endpoints will be determined:

- Change from baseline (CFB) in systolic and diastolic BP and pulse rate
- The minimum and maximum post-dose systolic and diastolic BP and pulse rate
- The maximum increase and decrease from baseline over all measurements taken post-dose for systolic and diastolic BP and pulse rate

The maximum increase from baseline will be calculated by selecting the maximum change from baseline over the respective period, except in the case where a participant does not show an increase. In such an instance, the minimum decrease should be taken. Similarly, the maximum decrease from baseline will be determined by selecting the minimum value of the change from baseline. In cases where a participant does not show a decrease, the minimum increase should be taken.

If 3 of more participants have unplanned measurements at the same timepoint these may be summarized in addition to the planned timepoints.

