3.2.4. Electrocardiogram Data

A single 12-lead ECG will be obtained on all participants at times detailed in the SoA given in the protocol. ECG endpoints include heart rate, QT interval, PR interval and QTcF and QRS

complex. If not supplied QTcF will be derived using Fridericia's heart rate correction formula [1].

QTcF (msec) = QT (msec) / (RR) $^{1/3}$ where RR (sec) = 60/HR (if RR not provided).

Baseline will be defined as the last measurement prior to administration of study treatment on Period 1 Day 1.

The following endpoints will be determined:

- Change from baseline in QT, QTcF, PR, QRS interval and heart rate
- The maximum post-dose QTcF, heart rate, PR and QRS interval
- The maximum increase from baseline over all measurements taken post-dose for QTcF, heart rate, PR and QRS values

The maximum increase from baseline will be calculated by selecting the maximum change from baseline over the respective period, except in the case where a participant does not show an increase. In such an instance, the minimum decrease should be taken.

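### The SAP defines maximum ECG and vital-sign changes over all post-dose readings, but its reporting rule leaves unplanned readings out of the continuous maximum-change tables

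*SAP*

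**What the plan says.** **Definitions.** SAP 3.2.4 lists as an ECG endpoint "The maximum increase from baseline over all measurements taken post-dose for QTcF, heart rate, PR and QRS values". SAP 3.2.3 does the same for vital signs: "The maximum increase and decrease from baseline over all measurements taken post-dose for systolic and diastolic BP and pulse rate". Neither separates planned from unplanned readings.

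**Continuous tables.** SAP 6.2.4 plans a table of these maxima: "Maximum increase from baseline for QTcF, heart rate, PR and QRS values will be summarized by treatment according to sponsor reporting standards". SAP 6.2.3 plans the vital-sign counterpart, beginning "Maximum decrease from baseline for supine systolic and diastolic blood pressures".

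**Categorical tables.** Each section then describes a further output, using the bands in SAP Appendix 2, and says that planned and unplanned post-dose time points both count in it.

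**Reporting rule.** SAP 6.2.3 ends: "Unplanned assessment will be listed but will be excluded from safety summary except for categorical summaries". SAP 6.2.4 ends with the same rule for ECGs: "Unplanned assessments will be listed but will be excluded from safety summary", again with categorical summaries as the sole exception.

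**A further sentence in 3.2.3.** "If 3 of more participants have unplanned measurements at the same timepoint these may be summarized in addition to the planned timepoints". SAP 6.2.3 does not refer to it.

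**The concern.** The maximum-change tables are summaries of a continuous quantity, so the exception for categorical summaries does not reach them. A programmer who follows 6.2.3 and 6.2.4 would filter out unplanned records before taking the maximum. The result would not be the endpoint that 3.2.3 and 3.2.4 define. The same report could then carry two values of one quantity: a participant in the QTcF category for increases above 60 ms, beside a maximum-increase table for that formulation that shows less, or nothing for that participant.

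Unplanned readings are often taken because something looked abnormal, so they may well hold the extreme value. Protocol 8.3.3 builds in one such source. When QTcF or QT crosses its threshold, "then 2 additional ECGs will be collected approximately 2 to 4 minutes apart to confirm the original measurement". Protocol 8.3 and 8.3.1.1 also allow unscheduled safety measurements and extra blood pressure and pulse readings.

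**Working it through.** The plan states no figure for this point, so there is none to reproduce. The check compares the texts, counts planned readings and applies both rules to example records.

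**1. Which readings enter each output, as written**

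| Output | Planned | Unplanned | Source |
|---|---|---|---|
| Endpoint definition of maximum change | yes | yes | SAP 3.2.3, 3.2.4 |
| Continuous maximum-change table | yes | no | SAP 6.2.3, 6.2.4, closing rule |
| Categorical table | yes | yes | SAP 6.2.3, 6.2.4 |
| Listing | yes | yes | SAP 6.2.3, 6.2.4 |

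The second row conflicts with the first and third.

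**2. Planned post-dose readings (Protocol 1.3, Schedule of Activities)**

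- ECG: pre-dose on Day 1 of Period 1 only, then Day 3 of the last period, plus early termination. Each completer has one planned post-dose ECG in four periods.
- With 12 completers: 12 × 4 = 48 participant-periods, of which 12 have a planned post-dose ECG and 48 − 12 = 36 do not. Period 4 is D, C, B and A for sequences 1 to 4 (Protocol Table 2), so each formulation has 12 / 4 = 3 planned post-dose ECGs. With 8 completers, two per sequence, it has 2.
- Vital signs: pre-dose on Day 1 of each period and Day 3 of the last period, plus early termination. Nothing is planned between dosing and 48 hours. The pre-dose readings of Periods 2 to 4 come at least 48 hours after the previous dose. SAP 6.2.3 carries them back to that dose only when they meet a categorical criterion.

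**3. Both rules applied to illustrative records** (values are assumed, not from the documents)

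- *Triggered repeats, last period.* Baseline QTcF 420 ms, planned Day 3 480 ms, repeats 486 and 483 ms. The trigger in Protocol 8.3.3 is met: 480 − 420 = 60 ms, and 480 is above 450. Planned only: +60 ms, in the 30–60 band. All readings: 486 − 420 = +66 ms, in the >60 band. The continuous table shows 60 while the categorical table counts a case above 60.
- *Unplanned ECG in Period 2.* Baseline 400 ms, unplanned Period 2 reading 463 ms, planned Period 4 reading 404 ms. All readings: 463 − 400 = +63 ms for the Period 2 formulation. Planned only: no value for that formulation, while the categorical table counts a case above 60.
- *Systolic pressure, last period.* Baseline 118 mm Hg, unplanned 84, planned Day 3 116. All readings: 84 − 118 = −34. Planned only: 116 − 118 = −2. The categorical table counts a decrease of at least 30.

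**The case against.** The strongest reply is that the exclusion was meant only for by-timepoint summaries, so that the specific definition in 3.2.3 and 3.2.4 governs the maxima. Both maximum tables also follow sponsor reporting standards, which may settle the matter. That may be the intention, but the SAP does not say so, and its one stated exception is for categorical summaries. The ambiguity stands.

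The reply also limits the reach of the point, and these parts stand:

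- The maximum-QTcF analysis in Protocol 9.3.5.1 is itself categorical, and SAP 6.2.4 counts all readings there. Only the continuous maximum tables are in doubt.
- Unplanned values are listed, participants meeting the sponsor's abnormality criteria get individual profiles, and post-dose QTcF above 500 ms has its own listing. A reader might infer that safety signals would be hidden; the documents do not support that.
- For vital signs, the sentence in 3.2.3 about three or more participants is an optional exception, so a reader should not infer that unplanned readings are barred from every non-categorical summary. It concerns added timepoints, and it does not restore those readings to the maximum tables.

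Two stronger quantitative readings also fail. A reader might take 36 of 48 (75%) as the share of data affected. It is a fact about the schedule, it leaves out early-termination ECGs, and it says nothing about how many unplanned readings occur. A reader might also treat a planned ECG and its two repeats as exchangeable and conclude that a repeat is the maximum two times in three. The repeats are taken because the first value was high, so they tend to fall back, and that probability does not apply.

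**Conclusion.** The inconsistency is real but minor. As written, the continuous maximum-increase and maximum-decrease tables for ECG and vital signs would depart from their own definitions and could contradict the categorical tables. The sparse schedule gives it practical weight: apart from early termination, an acute change between dosing and 48 hours can appear only in an unplanned reading.

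The frequency and average size of the discrepancy cannot be derived, because the documents give no rate of unplanned readings and no QTcF or blood pressure variability. The example differences (6 ms in QTcF, a missing value, 32 mm Hg in systolic pressure) show what can happen, not what to expect. The conclusion rests on a literal reading of the closing sentences of 6.2.3 and 6.2.4. Safety is a secondary objective, and the primary PK analysis is unaffected.

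**What to change.** - In SAP 6.2.3 and 6.2.4, replace the closing rule with: unplanned assessments are listed and are excluded from by-timepoint summaries and mean plots only; they are included in maximum and minimum post-dose values, maximum changes from baseline, and categorical summaries.
- In SAP 3.2.3, limit the sentence about three or more participants to by-timepoint tables, and cite it in 6.2.3 as an exception to the exclusion.

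The cost is one sentence in each of two sections, a small edit in 3.2.3 and a change to a record filter. No new data are needed. The downside is that participants with extra readings have more chances of an extreme maximum; the categorical tables already have this property, so the two sets of tables would agree.
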